#### **Section 5: Sexual Behavior (primary, secondary, tertiary outcome variables)**

The next questions ask you about your sexual behavior.

5.1 Have you ever had sexual intercourse? Yes No

*If you have never had sexual intercourse, skip to Section 6.*

5.2 How old were you when you had sexual intercourse for the first time?

- a. I have never had sexual intercourse
- b. 11 years old or younger
- c. 12 years old
- d. 13 years old
- e. 14 years old
- f. 15 years old
- g. 16 years old
- h. 17 years old or older

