### **6.3.2. List of Data Source Materials and Measures (Table 2 below).**

**Student Survey:** To assess students' participation in N/E, we draw from several existing measurements that have been implemented and validated in research studies with AI youth. Primary outcome measure: Condom use will measure frequency of condom use relative to frequency of sex during sexual intercourse using questions derived from the Risk Behavior Assessment. Secondary outcome measures: These will include the number of sex partners; age of onset of sexual intercourse; frequency of sexual intercourse; pregnancy history; frequency and type of birth control used during sexual intercourse relative to the frequency of sexual intercourse; and frequency and types of substance use (cigarettes, marijuana, alcohol, and methamphetamine). Tertiary outcome measures: Parent/legal guardian communication is measured by the frequency and types of SRH topics that parent/legal guardian and child discussed. Cultural identity is measured using two established measurements: One measure assesses the extent to which a student identifies with his or her American Indian culture and feels cultural pride, and the other measure assesses frequency and type of participation in cultural activities. Access to SRH services is measured by frequency and type of SRH service used (ever been tested for STIs and follow-up, ever been tested for HIV and follow-up, ever been tested for HCV and follow-up, ever been pregnant/gotten someone pregnant and follow-up). Other variables to be measured in N/E that assess attitudes, intentions, skills, and mental health are: Motivation to avoid STIs, HIV, HCV, and pregnancy, as measured by asking students how important it is to them to keep themselves (or someone else) from getting an STI, HIV, and HCV, and how important it is to them to keep from getting pregnant or getting someone pregnant. Intention to use condoms and/or birth control is measured by asking students how likely it is they will use condoms and/or birth control the next time they have sexual intercourse. Intention to abstain from sex is measured by asking students how likely it is that they will not participate in sexual intercourse. Condom and birth control use self-efficacy is measured by assessing confidence in one's ability to use condoms and birth control. Refusal skills regarding sex are assessed by how strongly students believe they can say no to sex. Knowledge about STIs, HIV, HCV, pregnancy, and healthy relationship characteristics are measured using true/false/don't know questions. Mental health is assessed using two established measures: One measure assesses depression using the C-ESD, and the other measurement assesses exposures to stressful life events by assessing lifetime occurrences of a series of negative events. Standard demographic measures in the student survey are age, gender, sexual orientation, school, and highest grade completed.

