H1: AI youth who participate in N/E will demonstrate increased condom use at 3, 9, and 12 months. (12 months will be used in the Primary Outcome analysis; 3 and 9 months will be used in the Secondary Outcomes analysis.) H2: AI youth who participate in N/E will demonstrate increased use of other birth control at 3, 9, and 12 months. They also will demonstrate a decrease in sexual risk behaviors as measured by reduced number of sex partners, delayed onset of sexual intercourse, and decreased substance use during sex, at 3, 9, and 12 months. (Secondary Outcomes) H3: N/E parents/legal guardians and youth will demonstrate significantly increased communication about topics related to SRH at 3, 9, and 12 months. AI youth who participate in the cultural mentoring program will demonstrate significantly increased understanding of cultural values related to traditional AI beliefs regarding SRH at 3, 9, and 12 months. And AI youth who participate in N/E will report significantly increased use of SRH services at 3, 9, and 12 months as a result of improved coordination among education, health care, and social service agencies on the Fort Peck Reservation. (Tertiary Outcomes) AIM 3: Evaluate the fidelity and acceptability of N/E. N/E's fidelity and acceptability will be evaluated using qualitative methods, including focus groups, activity logs, and staff field notes and meetings.

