5.12 Have you ever been tested for HIV, the virus that causes AIDS?

- a. Yes
- b. No
- c. Not sure

5.13 Have you ever been tested for other sexually transmitted diseases (STDs), such as genital herpes, chlamydia, syphilis, or genital warts?

- a. Yes
- b. No
- c. Not sure

5.14 Have you ever been told by a doctor or nurse that you had the HIV infection or any other sexually transmitted disease (STD)?

- a. Yes
- b. No
- c. Not sure

If yes, did you receive follow-up care? Yes No Not sure

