5.15 Have you ever been tested for HCV (Hepatitis C)?

- a. Yes
- b. No

c. Not sure

5.16 Have you ever been told by a doctor or nurse that you had Hepatitis C?

- a. Yes
- b. No
- c. Not sure

If yes, did you receive follow-up care? Yes    No    Not sure

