## Section 6: Substance Use Questions (secondary outcome variables)

These next questions are about alcohol and drug use.

6.1 How old were you when you tried any of the following for the first time?

Alcohol	I have never tried	8 years old or younger	9 or 10 years old	11 or 12 years old	13 or 14 years old	15 or 16 years old	17 years old or older
Marijuana (grass, pot, weed, or reefer)	I have never tried	8 years old or younger	9 or 10 years old	11 or 12 years old	13 or 14 years old	15 or 16 years old	17 years old or older
Meth (speed, crystal, crank, or ice)	I have never tried	8 years old or younger	9 or 10 years old	11 or 12 years old	13 or 14 years old	15 or 16 years old	17 years old or older
Cocaine (powder, crack, or freebase)	I have never tried	8 years old or younger	9 or 10 years old	11 or 12 years old	13 or 14 years old	15 or 16 years old	17 years old or older
Ecstasy (MOMA)	I have never tried	8 years old or younger	9 or 10 years old	11 or 12 years old	13 or 14 years old	15 or 16 years old	17 years old or older
Heroin (smack, junk, or diesel)	I have never tried	8 years old or younger	9 or 10 years old	11 or 12 years old	13 or 14 years old	15 or 16 years old	17 years old or older
Steroids (pills or shots without a doctor's prescription)	I have never tried	8 years old or younger	9 or 10 years old	11 or 12 years old	13 or 14 years old	15 or 16 years old	17 years old or older
Inhalants (sniff glue, breathe the contents of aerosol spray cans, or inhale any paints or sprays to get hiQh)	I have never tried	8 years old or younger	9 or 10 years old	11 or 12 years old	13 or 14 years old	15 or 16 years old	17 years old or older

6.2 During your life, how many times have you used any of the following:

Alcohol	0 times	1-2 times	3-9 times	10-19 times	20-39 times	40-99 times	100 or more times
Marijuana (grass, pot, weed, or reefer)	0 times	1-2 times	3-9 times	10-19 times	20-39 times	40-99 times	100 or more times
Meth (speed, crystal, crank, or ice)	0 times	1-2 times	3-9 times	10-19 times	20-39 times	40-99 times	100 or more times
Cocaine (powder, crack, or freebase)	0 times	1-2 times	3-9 times	10-19 times	20-39 times	40-99 times	100 or more times
Ecstasy (MOMA)	0 times	1-2 times	3-9 times	10-19 times	20-39 times	40-99 times	100 or more times
Heroin (smack, junk, or diesel)	0 times	1-2 times	3-9 times	10-19 times	20-39 times	40-99 times	100 or more times

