- g. You feel closer to your partner when you don't use condoms.
  - i. Disagree
  - ii. Neither Disagree nor Agree
  - iii. Agree
- h. If I decided to have sexual intercourse with someone, I'm quite certain I could get my partner to agree to use condoms.
  - i. Disagree
  - ii. Neither Disagree nor Agree
  - iii. Agree
- i. If my partner wanted to use a condom, we could use one correctly.
  - i. Disagree
  - ii. Neither Disagree nor Agree
  - iii. Agree
- j. I would never talk to a sex partner about using condoms.
  - i. Disagree
  - ii. Neither Disagree nor Agree
  - iii. Agree

8.3 The next few questions are about Hepatitis C (HCV). Answer True or False.

a. HCV has no long-term effects on your health.....	True	False
b. It is possible to be vaccinated against HCV.....	True	False
c. People who have injected drugs are not at risk for HCV.....	True	False
d. HCV can be transmitted by tattooing and body piercing.....	True	False
e. All people who have HCV can be cured.....	True	False
f. HCV can be transmitted by sharing razors or toothbrushes.....	True	False
g. A person can get HCV by sharing a needle and syringe with someone when injecting drugs.....	True	False
h. A woman can get HCV through having sex with a man.....	True	False
i. A person can get HCV from mosquitos.....	True	False
j. Someone who looks very healthy can pass on HCV.....	True	False

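### The skip after survey item 5.1 leaves STI, HIV and HCV testing unrecorded for students who have never had intercourse, so part of the tertiary service-use outcome covers a subgroup that changes with sexual onset

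*Combined protocol and SAP*

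**What the plan says.** - **Routing.** Below student survey item 5.1 (ever had intercourse) stands "If you have never had sexual intercourse, skip to Section 6". The destination is headed "Section 6: Substance Use Questions".
- **Items passed over.** Item 5.12 asks "Have you ever been tested for HIV, the virus that causes AIDS", and 5.13 asks the same about other STDs. Item 5.15 asks "Have you ever been tested for HCV (Hepatitis C". Items 5.14 and 5.16 ask about diagnosis and, if there was one, follow-up care.
- **Outcome definition.** Section 6.3.2 names the tertiary service-use components: "ever been tested for STIs and follow-up, ever been tested for HIV and follow-up, ever been tested for HCV and follow-up", plus pregnancy with follow-up. Table 2 gives the outcome nine items without listing them.
- **Population.** H3 in the registration record (Study Description) reads "AI youth who participate in N/E will report significantly increased use of SRH services" at 3, 9 and 12 months. It is not limited to sexually experienced youth.
- **Onset as a target.** H2 in the same record expects delayed onset of intercourse.
- **Items asked of everyone.** Survey Section 4 precedes the skip and is labelled a tertiary outcome. Item 4.1 asks about ever having gone to the Indian Health Service or Fort Peck Tribal Health for condoms, birth control, a pregnancy test or an STD test. Items 4.2 to 4.5 cover where the student would go, comfort, satisfaction and intention.
- **Missing data.** Section 3.1.2 models dropout between survey occasions and imputes by matching to students with observed values. It does not mention items skipped by design.

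**The concern.** The hypothesis is about all participating youth, but the components that Section 6.3.2 uses to measure it are asked only of students who report intercourse. The systems-level component in Section 6.3 aims to improve STI, HIV and HCV screening for 15- to 18-year-olds and does not limit this to the sexually active. Testing of a never-active student is therefore something N/E could change, and these items would not record it.

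The set of students asked is also not fixed. A student who starts intercourse between surveys joins the denominator. Because N/E is expected to delay onset, entry can differ between intervention and control periods. A comparison of recorded testing proportions would then mix any effect on testing with an effect on who is asked.

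**Working it through.** **1. Tracing the form for a student who answers 'No' at 5.1**

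| Content | Item | Asked? |
|---|---|---|
| Pregnancy | 5.11 | No |
| HIV test | 5.12 | No |
| Other STD test | 5.13 | No |
| HIV/STD diagnosis, follow-up care | 5.14 | No |
| HCV test | 5.15 | No |
| HCV diagnosis, follow-up care | 5.16 | No |
| Ever attended two named services | 4.1 | Yes |

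Counting the two follow-up questions separately, 5.11 to 5.16 hold eight questions. Adding 4.1 gives nine, which is one possible reading of Table 2; the documents do not confirm it. On that reading, one of nine is answered by never-active students.

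**2. Students asked.** The plan's own figure first (Section 3.1.1, powered on condom use): 292 × 1.3273 = 387.57, and 387.57 / 0.85 = 455.97, so 456. Expected completers are 456 × 0.85 = 387.6, about 388. The ever-active share f is not in the documents; 30% to 70% is an assumption.

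| f | Asked at baseline, 456 × f | Asked at 12 months if nobody new starts, 387.6 × f |
|---|---|---|
| 0.30 | 137 | 116 |
| 0.50 | 228 | 194 |
| 0.70 | 319 | 271 |

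**3. Precision.** With independent students and unchanged variance, the standard error is multiplied by 1/√f: 1.41 at f = 0.50. Clustering reduces this. For a school mean the variance is proportional to (1 + (n − 1)ρ)/n. With the plan's ρ = 0.016 and 388/5, about 78 completers per school:

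- n = 78: (1 + 77 × 0.016)/78 = 0.02862
- n = 39: (1 + 38 × 0.016)/39 = 0.04123
- multiplier: √(0.04123/0.02862) = 1.20

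**4. Bias from a changing denominator.** Let s be the share ever active at baseline, g the share who start later, q_o the ever-tested rate in the first group and q_n the rate in the second. With nobody's testing status changing, the recorded proportion moves by

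g(q_n − q_o)/(s + g).

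Assume q_o = 0.40, q_n from 0.10 to 0.20, s from 0.30 to 0.70 and g from 0.05 to 0.15. The spurious shift then runs from −1.3 points (s = 0.70, g = 0.05, q_n = 0.20) to −10.0 points (s = 0.30, g = 0.15, q_n = 0.10).

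That is a change over time within one group. The mixed model in Section 3.1.5 has a fixed time effect, which is there to absorb shifts common to all schools. What matters for the intervention effect is a difference in g between conditions. Take s = 0.50, q_o = 0.40 and q_n = 0.10, with g = 0.10 under control and 0.05 under N/E:

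- control: (0.50 × 0.40 + 0.10 × 0.10)/0.60 = 0.350
- N/E: (0.50 × 0.40 + 0.05 × 0.10)/0.55 = 0.373

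The difference is +2.3 points in favour of N/E with no effect on testing. If new starters were tested more often than the others (q_n > q_o), the sign would reverse. All rates here are assumptions.

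**The case against.** **The outcome is not wholly missing.** A reader might infer that service use is unobserved for never-active students. That goes too far: Section 4 is asked of everyone, is labelled a tertiary outcome, and item 4.1 records some actual use, including attendance for an STD test. This stands. But 4.1 combines several reasons at two providers and asks nothing about HIV testing, HCV testing or follow-up care, so it does not replace the components named in Section 6.3.2.

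**A reversed effect is not shown.** A reader might infer that the service-use effect could come out with the wrong sign, since the number tested can rise while the recorded proportion falls. Such an example is a before/after contrast in one group, with no comparator and no time effect. Delayed onset with mostly untested starters would in fact exaggerate benefit. The documents support possible bias, not its direction.

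**The plan does not say skipped items will be imputed.** Section 3.1.2 concerns dropout and is silent on structural skips. The gap is a missing rule. If its matching step were applied to these items, every donor would be sexually experienced.

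**A skip could mean an implied 'no'.** No section says so. The true/false statement "HCV can be transmitted by tattooing and body piercing" in survey Section 8 does not settle it either, because it is a knowledge question listed beside the statement that mosquitos transmit HCV. The better argument is that H3 and the systems component set no such limit.

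**The live branching may differ.** Surveys run in REDCap, whose branching is not shown, and items 5.2 and 5.9 offer a never-had-intercourse option that the printed skip makes redundant. This is a fair caution; the built form should be checked against the printed one.

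**Conclusion.** The point holds for the testing and follow-up components of a tertiary outcome. As printed, the form does not record them for never-active students, although H3 covers all participating youth, and no scoring or population rule compensates. An analysis of available answers loses precision and can be biased, because the group asked depends on onset, which H2 expects N/E to change. That conclusion rests on the printed routing being used and on skipped answers being left missing.

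The size and direction cannot be determined from the documents. The counts of 137 to 319 asked at baseline, the 1.20 multiplier for a school mean when half are asked, and the shifts of a few points are illustrations on assumed shares and rates. The documents do not support calling the whole outcome missing or predicting a reversed effect. The primary condom-use analysis and N = 456 are unaffected.

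**What to change.** **Surveys not yet fielded.** Change the branching so that 'No' at 5.1 goes to item 5.12 instead of Section 6, and analyse testing over all surveyed students. Record which version of the form each student answered, because moving from skipped answers scored 'no' to answers actually asked can look like a rise in testing.

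**Surveys already fielded with the skip.** Section 4.1 planned baseline for March to June 2019 and Wave 1 follow-up from December 2019, and the package contains IRB memoranda from 2020, so some surveys may be past changing. For these:

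- report the number tested over all surveyed students, scoring skipped answers 'no' as a stated assumption;
- add a sensitivity analysis limited to students ever active at baseline, a group that does not change with later onset;
- do not impute skipped items from sexually experienced donors.

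**Plan text.** List the nine items in Table 2 and state how each is scored when skipped.

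**Cost.** One REDCap branching rule, a minor IRB notice, about five more items for never-active students and a short addition to Section 3. No change to sample size or the primary analysis.

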be developed based on the multi-level components derived from the Ecological Systems Theory model

upon with the N/E was built. CFAs and SEMs will be conducted using Mplus software.

**3.1.5 Randomization of schools.** The 5 schools that AI youth from Fort Peck attend are the clusters to be randomized into the intervention, with all schools eventually being randomized to the intervention. Students and their parents/legal guardians will be recruited for baseline participation prior to randomization of the sites. Schools will be randomized to the intervention following baseline data collection using a single sequence random assignment to clusters that will determine order of intervention receipt.

**3.1.5 Generalized linear mixed-effects models.** To test for effectiveness of the *NIE* intervention across all hypotheses under Aim 2, the generalized linear mixed-effects models (GLMM) will be used to model binary primary and secondary outcomes (condom use under H1, condom use and other sexual risks under H2) and continuous tertiary outcomes (H3) in the data. The GLMM allows for individual-level binary and continuous responses to be modeled, key covariates to be controlled for, the specification of autocorrelation within individuals, and clustering by school. The GLMM is also the most frequently employed analytic method to adjust for the longitudinal nature of SWDs, and it was chosen over the Generalized Estimating Equations (GEEs) because GEEs show inflated Type 1 error rates when the number of clusters is small, as is the case with the number of schools at Fort Peck. Hussey and Hughes proposed a mixed-effects regression approach for the SWD-CRT design, where:

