## **SECTION 5: SELECTION AND ENROLLMENT OF PARTICIPANTS**

**4.1 Inclusion Criteria.** To be eligible for inclusion in *N/E*, students must be: 1) 15 to 18 years old; 2) a registered member of a federally recognized tribe or an associate tribal member; and 3) a resident of Fort Peck with a parent/legal guardian. For inclusion in the systems-level component of *N/E*, only those staff members who sit on the Epi Team as representatives of their respective agencies are eligible. Written informed consent will be obtained from the head of each agency represented on the Epi Team and the staff member participating in the Epi Team.

**4.2 Exclusion Criteria.** Exclusion criteria are minimal due to the CAB's value of inclusion in *N/E*. Exclusion criteria include: 1) not meeting the aforementioned inclusion criteria; and 2) having a medically identified physical or cognitive impairment that would impede their understanding of and participation in the educational content and activities of *Native Stand*, *Native Voices*, and the cultural mentoring program.

**4.3 Study Enrollment Procedures.** Students and their parent/legal guardian will be recruited from each of the study's 5 schools. Based on discussions with school personnel and our previously successful recruitment strategies, recruitment will occur via flyers posted in the schools, letters to the parents, parent-teacher meetings, and word of mouth. Additionally, a parent/legal guardian session that provides an overview of *N/E*, the content and format of the intervention components, and risks and benefits of participation will be held at each of the study's 5 schools. Students and their parents/legal guardians, and students from each cluster, will be recruited for participation at baseline. Students and their parents/legal guardians will be recruited for baseline participation **prior to randomization of the sites**. Students and parents/legal guardians will be assigned unique study identification numbers. No persons who refuse to participate in the study, in whole or in part, will be coerced to engage in any study activity. After written consent and assent is obtained from the parent/legal guardian and child, respectively, they will be enrolled in the study.

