**Table 2. NIE Measures.**

**Table 2. N/E Measures.**

Data Collection Instruments and Measures	Data Collection: Baseline & Months				Description of Measures Number of Items; Scale Anchors; Benchmark Values	
	Base	3	9	12		
Student Survey						
Primary Outcome Variable						
Proportion of condom use during sexual intercourse (SI)	X	X	X	X	2 items; number of times condom used relative to number of times had SI	
Secondary Outcome Variables						
Age of onset of sexual intercourse	X	X	X	X	2 items; ever had SI & age at first SI	
Number of sex partners	X	X	X	X	2 items; lifetime & past-month sex partners	
Frequency of sexual intercourse	X	X	X	X	1 item; frequency of SI in past month	
Pregnancy history	X	X	X	X	1 item; number of pregnancies	
Type & frequency of birth control (BC) during sexual intercourse	X	X	X	X	3 items; type of BC use and number of times BC used during SI	
Type & frequency of substance use (SU) during sexual intercourse	X	X	X	X	1 item measures SU with SI; 5 items measure lifetime and past month SU	
Tertiary Outcome Variables						
Type & frequency of parent/legal guardian-child SRH communication	X	X	X	X	24 items Likert scale; higher score = higher communication	
Cultural identity & participation in cultural activities	X	X	X	X	3 items cultural identity ( $\alpha = .75$ ); 2 items cultural activities engagement ( $\alpha = .46$ )	
Type & frequency of SRH services	X	X	X	X	9 items; frequency, type, and follow-up of SRH services used	
Other Variables						
Motivation to avoid STIs, HIV, HCV, & pregnancy	X	X	X	X	Up to 9 items; 1 (very true) to 5 (very untrue); 1 = more positive attitude/motivation	
Condom & birth control use intention & self-efficacy	X	X	X	X	4 items per intention; 1 (very true) to 5 (very untrue); 1 = higher intention; 6 self-efficacy items; 1 (very easy) to 4 (very hard); 1 = high self-efficacy	
Abstinence	X	X	X	X	3 items; 1 (strongly disagree) to 4 (strongly agree); 4 = more supportive of teen abstinence	
Refusal skills regarding sex	X	X	X	X	7 items; 1 (I definitely can say no) to 5 (I definitely can't); 1 = stronger refusal skills	
Knowledge of STIs, HIV, HCV, pregnancy, & health relationships	X	X	X	X	Range of 4 to 10 items per topic; True/False/DK; Average proportion of questions correct	
Depression (CES-D) & exposure to stressful life events	X	X	X	X	CES-D — 7 items ( $\alpha = .80$ ); Life Events — 24 items; Yes/No; number of events observed	
Student Demographics						

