### Secondary Outcome Measure:

2. Change in delayed onset of sexual intercourse at 3 months, 9 months and 12 months

Changes in delayed onset of sexual intercourse will be measured intercourse with 2 items (ever had sexual intercourse and age at first sexual intercourse)

[Time Frame: 3 months, 9 months and 12 months]

3. Change in decreased number of sex partners at 3 months, 9 months and 12 months  
Change in decreased number of sex partners will be measured by 2 items ( lifetime of sex partners and the number of sex partners in the past month)  
[Time Frame: 3 months, 9 months and 12 months]
4. Change in frequency of sexual intercourse at 3 months, 9 months and 12 months  
Change in frequency of sexual intercourse will be measured with 1 time ( frequency of sexual intercourse in the past month)  
[Time Frame: 3 months, 9 months and 12 months]
5. Change in number of pregnancies at 3 months, 9 months and 12 months  
Change in number of pregnancies will be measured with 1 item (number of pregnancies)  
[Time Frame: 3 months, 9 months and 12 months]
6. Change in increased use of birth control during sexual intercourse at 3 months, 9 months and 12 months  
Change in the increased use of birth control during sexual intercourse will be measured with 3 items (type of birth control used and number of times birth control was used during sexual intercourse)  
[Time Frame: 3 months, 9 months and 12 months]
7. Change in decreased alcohol/drug use concurrently sexual intercourse at 3 months, 9 months and 12 months  
Change in decreased alcohol/drugs used concurrently with sexual intercourse will be measured with 1 item ( substance use with sexual intercourse)  
[Time Frame: 3 months, 9 months and 12 months]

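### The two onset items often cannot place first intercourse before or after a school's start when it occurs between baseline and the 3-month survey, and the age item pools 17 and over

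*Combined protocol and SAP*

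**What the plan says.** Table 2 defines the onset outcome as "2 items; ever had SI & age at first SI", collected at baseline, 3, 9 and 12 months. The registry record (Secondary Outcome Measure 2) uses the same pair: "ever had sexual intercourse and age at first sexual intercourse".

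In the student survey the first item is "5.1 Have you ever had sexual intercourse? Yes No". The second, "How old were you when you had sexual intercourse for the first time", offers single years from 12 to 16 and ends at "h. 17 years old or older". Current age (item 1.2) is also recorded in years, and the demographic items shown include no date of birth.

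Under the inclusion criteria, "students must be: 1) 15 to 18 years old". Section 4.1 puts baseline for all schools between mid-March and June 2019. Section 2.3.5 then surveys students 3, 9 and 12 months after their own school begins. No student survey is described between baseline and that start.

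The generalized linear mixed-effects models subsection of Section 3 says the GLMM "will be used to model binary primary and secondary outcomes", with an intervention indicator X_ij. It does not say how items 5.1 and 5.2 combine, which students are at risk of onset, or how an onset is assigned to control or intervention time.

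**The concern.** Only students not yet active at baseline can show a delay. For them the analysis needs to know whether first intercourse came before or after their school began N/E. Having ever had intercourse is irreversible, so a student who started while the school was still a control first appears as a yes at the 3-month survey, when X_ij = 1. The longer the wait between baseline and start, the more onset of this kind accumulates, and it accumulates most in the late-wave schools. Age at first intercourse is the only other item shown that could date the event. It is coarse, and its open top category begins at an age that many students will have reached before their school starts.

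**Working it through.** **Inputs.** Answer list of item 5.2 and whole-year age (student survey); ages 15 to 18 (inclusion criteria); baseline window (Section 4.1); survey schedule and wave dates (Section 2.3.5). The plan gives no figure for onset to reproduce, because the power analysis in Section 3.1.1 concerns condom use only.

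**Assumptions.** Baseline taken as May 2019; September starts; closed cohort; ages uniform. The documents give no age distribution and no share already active at baseline.

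**Step 1: what the items can place.**

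| Onset interval | Repeated item 5.1 | Item 5.2 |
|---|---|---|
| Before baseline | Yes at baseline | Age, pooled from 17 |
| Baseline to 3-month survey | Placed in the interval, but the interval straddles the start | Whole years, pooled from 17; often cannot split the interval |
| 3 to 9 months, 9 to 12 months | Placed, and known to be after the start | Not needed |
| Not yet | Still no, at any age | Not applicable |

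**Step 2: the unresolved gap.** Untreated months = May 2019 to start; gap = untreated months + 3.

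| Start | Untreated | Gap | Untreated share |
|---|---|---|---|
| Sept 2019 | 4 | 7 | 4/7 = 57% |
| Sept 2020 | 16 | 19 | 16/19 = 84% |
| Sept 2021 | 28 | 31 | 28/31 = 90% |

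The 2019 row is Wave 1, and Section 4.1 agrees with it: the first follow-up is in December 2019. Waves 2 and 3 depend on the reading. Section 2.3.5 gives 2019-2020 and 2020-2021, while Section 4.1 spreads three waves over the next 3 years. Wave 2 may therefore sit in the first or second row, and Wave 3 in the second or third.

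**Step 3: how many students are 17 or over at the start.** With s = years from May 2019 to start, the share is (upper age + s − 17) / age range, capped at 1.

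- Ages 15.0-18.99: (19 + 0.333 − 17)/4 = 58% at September 2019; (19 + 1.333 − 17)/4 = 83% at 2020; 100% at 2021.
- Ages 15.0-17.99: (18 + 0.333 − 17)/3 = 44%; (18 + 1.333 − 17)/3 = 78%; 100%.

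Taking baseline as mid-April instead gives 59%, 84% and 100% (46%, 79%, 100%). With equal school sizes, the mid-April whole-cohort share runs from 0.6 × 0.459 + 0.4 × 0.793 = 59% (starts 2019/2019/2020, ages to 17.99) to 0.2 × 0.595 + 0.4 × 0.845 + 0.4 × 1 = 86% (starts 2019/2020/2021, ages to 18.99). These are shares of all students. The share among those not yet active is unknown.

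**Step 4: would a longer answer list be enough?** Take a hypothetical student aged 17 years 2 months in May 2019 whose school starts in September 2020. This student turns 18 in March 2020. As printed, any onset after baseline is 17 or over. With 18 listed separately, an answer of 17 means before March 2020 and so before the start. An answer of 18 at the December 2020 survey covers March to December 2020, of which 6 of 9 months precede the start. Without a birth date the analyst cannot fix even these limits. The longer list helps some students and leaves others unresolved.

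**Step 5: consequence in the model.** If ever/never is the response and X_ij = 1 at the 3-month survey, onset in the untreated months of Step 2 is counted under intervention.

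**The case against.** A reader might infer from the open category that the outcome cannot register a delay for most of the cohort. The documents do not support that. Onset is a two-item outcome, and item 5.1 records continued non-initiation at every survey and at any age. It also dates onset between the later surveys as post-start in every wave. Item 5.2 still registers delays up to 16, and from 16 to the 17-and-over category. A binary model of secondary outcomes fits item 5.1.

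A reader might also blame the top-code for the dating problem. The main causes are the missing survey between baseline and start, and ages in whole years.

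The percentages deserve caution too. They describe all students, whereas those not yet active may be younger, and students active at baseline have a fixed onset age whatever the coding. The figures for a 2021 start need the later reading of the wave dates.

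All of this stands, and it narrows the point. It does not reach the baseline-to-3-month gap, which item 5.1 cannot split and for which the plan gives no assignment rule.

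**Conclusion.** The point holds as a measurement and specification gap in one secondary outcome. Item 5.2 does not separate onset at 17 from later onset, and onset in the baseline-to-3-month interval often cannot be assigned to control or intervention time. With September starts counted from May 2019, the untreated part of that interval is 57%, 84% or 90% for a 2019, 2020 or 2021 start.

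Misassignment would tend to work against N/E, most in late-wave schools, if ever/never is modelled with X_ij = 1 at 3 months. Its size depends on how time is modelled, which the plan leaves open for this outcome. It would be too strong to call this a bias toward no effect: that follows only if N/E truly delays onset, and if N/E has no effect the same error could make it look harmful.

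The primary outcome and the sample size of 456 are untouched. The change is cheap and worth making.

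**What to change.** 1. At the 3-, 9- and 12-month surveys, ask each student newly answering yes to item 5.1 for the month and year of first intercourse.
2. State in the analysis plan that the outcome is incident onset among students never active at baseline, and how items 5.1 and 5.2 contribute to it.
3. Assign each onset to control or intervention time by the school's N/E start date. Where the month is missing, treat onset as interval-censored between the two surrounding surveys.
4. Extend item 5.2 to 17, 18, 19, and 20 or older. This is a supporting change and does not settle dating alone.
5. Reconcile the Wave 2 and Wave 3 dates in Sections 2.3.5 and 4.1 and record each school's actual start date, on which the rule depends.

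The cost is one added REDCap date field, an edited answer list, a short paragraph in the analysis plan and a minor IRB amendment. The downside is some recall error in the reported month.
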